Identifiers: NCT ID not yet assigned

Unique Protocol ID: WHO-PEN@Scale

Brief Title: Strengthening Primary Healthcare Delivery for Diabetes and Hypertension in Eswatini

Date of document: November 10th 2019

Statistical analysis plan:

We will test the following two null hypotheses for each outcome: i) participants in the intervention arms (arm 2 [PEN] and arm 3 [ePEN] combined) have the same outcome as participants in the standard-of-care arm; and ii) participants in arm 3 (ePEN) have the same outcome as participants in arm 2 (PEN). We will not adjust for multiple hypothesis testing in these analyses because each comparison answers a fundamentally different question. That is, the comparison of the standard-of-care arm with arm 2 and 3 combined answers what the effect was of scaling up the WHO-PEN package in primary care in Eswatini, and the comparison of arm 2 (PEN) with arm 3 (ePEN) answers what the effect was of involving community health workers in the WHO-PEN scale-up compared to not involving community health workers in the scale-up. In secondary analyses, we will also compare the standard-of-care arm to arm 3 (ePEN).

All primary analyses will exclude clusters in the cities of Manzini and Mbabane because we expect a high degree of contamination between the study arms in these two cities given the close proximity of healthcare facilities in these locations. However, we will include these clusters in secondary analyses.

We will use ordinary least squares regression to compare mean HbA1c among adults with diabetes and mean systolic blood pressure among adults with hypertension between the study arms. All regression models will regress the outcome onto an indicator for study arm, and adjust standard errors for clustering at the level of the unit of randomization (the primary healthcare facility and its catchment area). In the primary analysis, we will include participants' socio-demographic characteristics as co-variates, which we do not expect will substantially affect the

point estimates but may well reduce the variance (and thus increase power). In secondary analyses, we will run these regressions without adjusting for participants' socio-demographic characteristics. We will use a significance level of $p<0.05$ for all analyses. As a robustness check, the p-values for the effect estimates obtained from these regressions will be calculated using randomization inference, which is a permutation method that, unlike regression analysis, does not rely on parametric assumptions [1, 2]. Secondary endpoints will be analyzed using the same approach except that we will use modified Poisson regression with a robust error structure for binary outcomes.[3]

All analyses will include a sub-group analysis that compares the effect of the intervention(s) between men and women, whether or not a household was ever visited by a community health worker, whether or not a household was visited by a community health worker in the past 12 months, ten-year age groups, rural versus urban areas, the different regions (Hhohho, Lubombo, Manzini, and Shiselweni), and categories of educational attainment. In addition to disaggregating effects by these sub-groups, we will employ random forest analyses to identify sub-groups that were particularly likely or unlikely to benefit from the intervention. These techniques are a non-parametric data-driven way of identifying sub-groups.[4, 5]

References:

2. Heß S. Randomization inference with Stata: A guide and software. *Stata Journal*. 2017;17(3):630-51.
3. Zou G. A modified poisson regression approach to prospective studies with binary data. *American journal of epidemiology*. 2004;159(7):702-6. Epub 2004/03/23. PubMed PMID: 15033648.

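### The SAP names no small-sample method for its cluster-adjusted standard errors, and with the usual ones the region and rural/urban effect comparisons would reject well above 5% at every cluster count tried (24 to 120)

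*SAP*

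**What the plan says.** The SAP is one undivided text. For the continuous outcomes it states: "We will use ordinary least squares regression to compare mean HbA1c among adults with diabetes and mean systolic blood pressure among adults with hypertension". Each model is to "adjust standard errors for clustering at the level of the unit of randomization", that unit being the primary healthcare facility with its catchment area. For secondary endpoints the approach is the same, except that "we will use modified Poisson regression with a robust error structure for binary outcomes".

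On the decision rule: "We will use a significance level of $p<0.05$ for all analyses". On the permutation method: "As a robustness check, the p-values for the effect estimates obtained from these regressions will be calculated using randomization inference".

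The first null hypothesis is that "participants in the intervention arms (arm 2 [PEN] and arm 3 [ePEN] combined) have the same outcome as participants in the standard-of-care arm"; the second compares arm 3 with arm 2. Every analysis also carries a comparison of effects between sub-groups, including "rural versus urban areas, the different regions (Hhohho, Lubombo, Manzini, and Shiselweni"). The set of clusters is reduced beforehand: "All primary analyses will exclude clusters in the cities of Manzini and Mbabane".

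The text does not say which cluster-robust variance is meant, what reference distribution or degrees of freedom go with it, or which p-value decides if the regression and the permutation disagree. It states no number of clusters.

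**The concern.** Cluster-robust standard errors are consistent as the number of clusters grows. With few clusters, or clusters of unequal size, the usual versions are biased downward, and a normal or t(G-1) reference is too optimistic. What counts is the number of clusters that inform the particular coefficient, not the total.

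For the main contrasts all retained clusters contribute. For region and rural/urban the position is worse. These are attributes of the catchment area, or nearly so, so an interaction with arm is estimated from the clusters in each region-by-arm or urban-by-arm cell. Excluding the two cities from the primary analyses also removes clusters from the urban side.

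At stake is whether a reported difference in effect between regions, or between town and country, can be trusted at the stated 5% level. Such a finding could bear on where a scale-up programme is thought to work. Sub-groups by sex, age or education vary within clusters, and the figures below do not apply to them.

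**Working it through.** **Inputs from the SAP.** Significance level 0.05 (two-sided assumed); individual-level least squares; clustering by facility; three arms; four regions; rural/urban. There is no sample size, power or cluster count to reproduce.

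**Assumptions, not in the SAP.** Mean 20 participants per cluster, cluster-size CV 0.6, ICC 0.03, regions of equal size, 20% of clusters urban (at least 4), clusters allocated 2:1 for arms 2+3 against standard of care, arms balanced within sub-group strata, no covariates. The number of clusters G was varied.

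**Step 1: why the interactions suffer.** The plain sandwich variance is V = (X'X)⁻¹ [Σ X_g' e_g e_g' X_g] (X'X)⁻¹, summed over clusters g. With m equal clusters in a cell it recovers on average (m-1)/m of the variance of that cell's mean. The common software factor G/(G-1) gives almost nothing back. For one region's standard-of-care cell, m = (G/4) × 1/3:

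- G = 24: m = 2; (1/2) × (24/23) = 0.52 of the true variance
- G = 60: m = 5; (4/5) × (60/59) = 0.81
- G = 120: m = 10; (9/10) × (120/119) = 0.91

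The reference distribution is also wrong. For one region against another at G = 24, the Satterthwaite degrees of freedom averaged 3.7, against G-1 = 23. The 5% critical values are about 2.87 and 2.07.

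**Step 2: simulated size under the null.** Runs of 3,000 to 4,000 trials; Monte Carlo standard error √(0.05 × 0.95/3,000) = 0.4 points near 5%. Each range runs from the usual default (the finite-cluster factor with a t or F reference on G-1) to the plain sandwich with a z or chi-square reference. Arms 2+3 against standard of care:

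| Clusters in contrast | Main contrast | Region interaction (3 df) | Rural/urban interaction |
|---|---|---|---|
| 24 | 7.7-9.9% | 39-47% | 18-21% |
| 60 | 6.0-6.8% | 16-18% | 11-12% |
| 90 | 5.7-5.9% | 12-14% | 8.6-9.2% |
| 120 | 5.5-6.0% | 10-11% | 7.9-8.5% |

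A separate simulation of the default version gave 15.5%, 11.6% and 9.5% for the region interaction at 60, 90 and 120 clusters, and 10.3%, 8.4% and 7.9% for rural/urban. The rounded figures in the verdict agree with both to about a point.

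Arm 3 against arm 2 (1:1) behaves alike. The main contrast is 7.2-9.8% at 24 clusters and 5.5-6.0% at 80; the region interaction is 29-37% at 24 and 10-12% at 80.

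**Step 3: the remedies.** CR2 replaces e_g by (I - H_gg)^(-1/2) e_g, where H_gg is the cluster's block of the hat matrix, and takes its degrees of freedom from the Satterthwaite approximation. Simulated sizes:

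- main contrasts: 4.4-6.0% (12 to 90 clusters)
- one region against another: 4.1-6.3% (24 to 120)
- rural/urban interaction: 1.9-5.2% (24 to 90), the low value at 36 clusters

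Cluster-level permutation kept the main contrasts at 4.2-6.1% (12 to 90 clusters). The joint 3-df region test under CR2 and the modified Poisson models were not simulated.

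**The case against.** The strongest reply has four parts.

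*The SAP already plans a robust method.* Randomization inference is specified for the regression effect estimates, and it held the main contrasts near 5% in the check. This stands for the main contrasts, and a reader who infers that all p-values rest on cluster-robust errors would be wrong. It does not cover the rest. The permutation is a check with no governing rule, and the sub-groups come in a later paragraph that does not mention it. Permuting arm labels also tests the hypothesis of no effect at all. A test of equal effects across sub-groups needs something else.

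*Silence is not an error.* The clause excludes no estimator, CR2 included. That is true: a reader might infer that the SAP rules out a correction, and it does not. But it leaves open versions that give different p-values, and the usual software default is among those that fail for the interactions.

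*The cluster count is unknown and belongs to the protocol.* This also stands. A reader might infer that the main comparisons exceed 5% materially, or that the city exclusion and three arms in themselves make clusters few. The document supports neither without a count. With 60 or more clusters the default version exceeds 5% by about a point or less in the main contrasts. The interactions do not depend on the missing count in the same way, since no count up to 120 brought them near 5%.

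*Intervals.* One might add that the plan's confidence intervals are too narrow. The SAP never mentions intervals, so no stated interval method is at fault. Any interval built from the same standard errors would share the defect.

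**Conclusion.** The concern holds in a limited form. The SAP fixes a 5% level for all analyses but not the small-sample method needed to attain it. With the usual cluster-robust test and a t or F reference on G-1, the region interaction for arms 2+3 against standard of care has a size of about 38% at 24 clusters, 16% at 60, 12% at 90 and 10% at 120. The rural/urban interaction has about 17%, 10%, 8% and 8%. The main contrast has about 8% at 24 clusters and about 6% from 60 to 120, so it matters only if clusters are few.

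The exact sizes rest on the assumed cluster size, its variation, the ICC, equal regions, the 20% urban share and the allocation, and they leave out the covariates that the primary model includes. The ordering, with cluster-level sub-groups clearly worse than the main contrasts, held at every count tried. This should be changed in the SAP. It does not by itself undermine the two main hypothesis tests.

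**What to change.** Replace the clustering clause with wording such as: *standard errors will be adjusted for clustering by facility using the bias-reduced (CR2) estimator with Satterthwaite degrees of freedom; the joint test across the four regions will use the matching small-sample F test; modified Poisson models will use the analogous bias-corrected sandwich variance with a t reference. This applies to the main contrasts and to the region and rural/urban contrasts.*

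Add one sentence saying which p-value decides if the regression and the permutation disagree. For the two main contrasts only, making the cluster-level randomization-inference p-value the deciding one is an acceptable alternative. It should not be carried over unmodified to the interactions, for the reason given under the objection.

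The cost is a few sentences and available software. Intervals become slightly wider, negligibly so with many clusters. Where a sub-group has very few clusters the test turns conservative (simulated size down to 1.9% for the rural/urban interaction). That loss of power is a fair reflection of how little information such a sub-group holds.

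### The 0.05 level set for all analyses also reaches seven sub-group factors, which the stated reason for not adjusting does not cover (minor)

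*SAP*

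**What the plan says.** The opening paragraph of the SAP sets out the arm comparisons: "We will test the following two null hypotheses for each outcome". The two hypotheses are arms 2 and 3 combined against standard of care, and arm 3 against arm 2. The only statement on multiplicity follows directly: "We will not adjust for multiple hypothesis testing in these analyses because each comparison answers a fundamentally different question". The next sentence explains this reason for those two comparisons alone, beginning with "the comparison of the standard-of-care arm with arm 2 and 3 combined answers what the effect was".

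The regression paragraph sets the level: "We will use a significance level of $p<0.05$ for all analyses".

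The sub-group paragraph then begins: "All analyses will include a sub-group analysis that compares the effect of the intervention(s) between men and women". It goes on to six more factors, the first being "whether or not a household was ever visited by a community health worker". The others are a community health worker visit in the past 12 months, ten-year age group, rural or urban area, region (four named) and educational attainment. A data-driven search is added: "In addition to disaggregating effects by these sub-groups, we will employ random forest analyses to identify sub-groups".

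The sub-group paragraph gives no test, threshold or multiplicity rule of its own, and it does not call these results exploratory. The SAP does use the label secondary elsewhere: for standard of care against arm 3, for the analyses that include the two cities, for the regressions without covariates, and for the secondary endpoints.

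**The concern.** The level is worded to cover everything, and the sub-group comparison is worded to be part of everything. Taken together, the two sentences put seven sub-group comparisons per outcome and arm comparison under the unadjusted 0.05 rule. The argument for not adjusting is that different arm comparisons answer different questions. That does not carry over to seven splits of one and the same comparison.

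At stake is the standing of a sub-group result. A chance difference between regions, age groups or education levels could be reported as significant on the same footing as the effect of the scale-up itself. In an evaluation of a national primary-care programme, such a result could be read as guidance on where or for whom the package works. The SAP does not say that sub-group results will be used in that way; this is a possible consequence.

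**Working it through.** The SAP gives no family-wise error rate for the sub-group analyses, so there is no planned figure to reproduce.

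**Inputs from the SAP**
- Level per test: 0.05 (regression paragraph).
- Number of factors: 7 (sub-group paragraph).
- Family: the factors within one outcome and one arm comparison, because the hypotheses are stated per outcome and per comparison.

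**Assumptions, not in the SAP**
- One interaction test per factor, each holding its nominal level.
- No true effect modification by any factor.
- The correlation between tests, shown as a range.

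**Independent tests**
- Expected false positives: 7 × 0.05 = 0.35.
- Chance of at least one: 1 − 0.95^7 = 1 − 0.698 = 0.302, about 30%.

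**Equally correlated tests** (simulated two-sided normal tests at 0.05, 500,000 draws)

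| Assumed correlation | Chance of at least one false positive |
|---|---|
| 0 | 30.2% |
| 0.3 | 27.0% |
| 0.5 | 23.0% |
| 0.7 | 17.9% |

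If only the two health-worker-visit factors are correlated, at 0.5 up to almost 1, the figure is 29.7% down to 26.6%.

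**Limits of these figures**
- The simulation uses a single-contrast test for each factor. Joint tests for age, region and education have several degrees of freedom, so the correlated figures are only indicative for them. The independent figure depends only on the level and the number of tests, so it carries over.
- If the two health-worker-visit factors are left out, 5 tests remain: 1 − 0.95^5 = 0.226, about 23% if independent.
- One test per factor is the smaller count. Suppose age has 5 to 7 groups and education 3 to 5 (the SAP gives neither). Testing each level against a reference then gives 1 + 1 + 1 + 4 + 1 + 3 + 2 = 13 to 1 + 1 + 1 + 6 + 1 + 3 + 4 = 17 contrasts. Treated as independent, these give 1 − 0.95^13 = 48.7% to 1 − 0.95^17 = 58.2%. Contrasts that share a reference level are correlated, so these two figures are rough.
- The random forest, the secondary endpoints and the repeat analyses are not counted.

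**The case against.** The strongest reply is that the sub-group tests are inferred. The SAP names no interaction test, and comparing or disaggregating effects can be done with estimates and intervals alone. The sentence on the level stands among the regressions of outcome on arm, so a narrower scope is possible. The factors are named in advance, nothing presents them as confirmatory, and the protocol, which is not shown, may call them exploratory. Unadjusted sub-group tests are acceptable when so declared.

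Much of this stands. It makes the point minor and the percentages conditional. It does not remove the point, because the level is expressly set for all analyses and the next paragraph uses the same scope for the sub-groups. An exploratory label in the protocol would conflict with that rule unless the SAP were reworded.

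A reader might infer more than the document supports:
- **That the arm comparisons have an inflated error rate, or need adjustment across outcomes or comparisons.** Adding sub-group tests does not change the arm-level tests, and the SAP gives its reason for leaving the comparisons unadjusted.
- **That 23% is a lower bound.** It rests on an assumed correlation of 0.5, and stronger correlation gives less (17.9% at 0.7).
- **That random forest findings will be tested at 0.05.** No p-value is attached to them, and the method is described as a data-driven way to find sub-groups. Only an explicit exploratory label is absent.

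**Conclusion.** The point holds as a minor one. The SAP's rule on significance is too broad: read literally, it lets sub-group differences be declared significant like the arm comparisons, and the reason for not adjusting does not extend that far. The chance of at least one false-positive factor per outcome and arm comparison is about 30% with independent tests, and less with correlated ones. This rests on the literal scope of the 0.05 sentence, one interaction test per factor and no true effect modification. Conclusions about the arms are not affected.

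**What to change.** Replace the sentence on the significance level with wording to this effect:
- The unadjusted 0.05 level applies to the primary and secondary arm comparisons of each outcome, including the analyses with the two cities and the regressions without covariates. Naming these keeps a stated level for every arm-level analysis.
- Each sub-group factor is assessed with one joint interaction test per outcome and comparison, and estimates with confidence intervals are reported for all factors, whatever their p-values.
- Sub-group and random forest results are exploratory, with no claim of significance at 0.05.

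No formal multiplicity procedure, such as Benjamini-Hochberg, is needed once the results carry that label. The change needs no further data and takes no power from the arm comparisons. Its cost is that real heterogeneity, if present, could not be declared confirmatory from this trial.

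### Two sub-groups defined by community health worker visits are not limited to visits before roll-out, so their results may not be protected by randomisation

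*SAP*

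**What the plan says.** The SAP's sub-group paragraph opens: "All analyses will include a sub-group analysis that compares the effect of the intervention(s) between men and women". It then continues the list. Counting sex, there are seven variables, and two of them concern CHW contact: "whether or not a household was ever visited by a community health worker" and "whether or not a household was visited by a community health worker in the past 12 months". The other five are sex, ten-year age group, rural or urban area, region and educational attainment.

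The two visit variables get the same treatment as the other five. The SAP gives no date from which the 12 months are counted and no limit on how late a visit may fall to count as ever. Neither variable is labelled post-randomisation, descriptive or non-causal. Besides reporting separate effects by sub-group, the paragraph plans a data-driven search: "we will employ random forest analyses to identify sub-groups that were particularly likely or unlikely to benefit from the intervention". It lists no input variables for that search.

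The opening paragraph on hypotheses says that the comparison of arm 2 with arm 3 answers what "the effect was of involving community health workers in the WHO-PEN scale-up compared to not involving community health workers in the scale-up". Randomisation is by primary care facility with its catchment area, so each household takes the arm of its cluster.

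**The concern.** A sub-group effect is a randomised comparison only if the assigned arm does not change who belongs to the sub-group. Sex and age meet that condition plainly. CHW visits may not, because CHW involvement is the randomised difference between ePEN and PEN. If visit status comes from a survey after roll-out, a 12-month look-back may cover the intervention period, and ever visited would include any visit made during it.

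Two separate problems could follow if the arm changes who is visited:

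- **Selection.** If visiting is related to prognosis, visited households in ePEN and visited households in PEN are different kinds of household. The same holds for unvisited households.
- **Conditioning on the intervention.** If visits are how ePEN works, splitting by visit status holds fixed part of what was randomised. The stratum contrasts are then not effects of assignment, even when visiting has nothing to do with prognosis.

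At stake is the table that a reader would consult to ask whether CHW contact changes the effect, the question closest to the second hypothesis.

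**Working it through.** The SAP gives no standard deviation, visit rate or effect size, so there is no figure of its own to reproduce. The calculation below only illustrates possible size, and every input is an assumption.

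**Selection route: set-up.** The true effect is zero in every household. Severity Z is standard normal. The outcome is SD × (r × Z + independent noise), with systolic pressure SD = 20 mmHg and r = 0.1 to 0.3. The chance of a visit is expit(a + ln(OR) × Z), where OR is the odds ratio of a visit per SD of severity and a is solved to give the stated visit rate. Random visiting is OR = 1. Then:

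- stratum bias (ePEN minus PEN) = SD × r × (E[Z | stratum, ePEN] − E[Z | stratum, PEN])
- false difference = bias in visited − bias in unvisited

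The multiplier SD × r is 20 × 0.1 = 2 at the low end and 20 × 0.3 = 6 at the high end.

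**Scenario 1: targeting differs.** PEN 30% visited at random; ePEN 60% visited, OR 1.5. Mean Z is 0 in both PEN strata. In ePEN it is +0.156 in visited and −0.234 in unvisited households.

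**Scenario 2: same targeting, different rates.** OR 1.5 in both arms; PEN 30%, ePEN 70%. Mean Z in visited households is 0.275 in PEN and 0.118 in ePEN, a change of −0.157. In unvisited households it is −0.118 and −0.275, also −0.157.

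**Scenario 3: equal rates, different targeting.** 30% visited in both arms, random in PEN, OR 1.5 in ePEN. Mean Z is 0 in both PEN strata, against +0.275 (visited) and −0.118 (unvisited) in ePEN.

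| Scenario | Visited, mmHg | Unvisited, mmHg | False difference, mmHg |
|---|---|---|---|
| 1, r = 0.1 | +0.31 | −0.47 | +0.78 |
| 1, r = 0.3 | +0.94 | −1.41 | +2.34 |
| 2, r = 0.1 | −0.31 | −0.31 | 0 |
| 2, r = 0.3 | −0.94 | −0.94 | 0 |
| 3, r = 0.1 | +0.55 | −0.24 | +0.78 |
| 3, r = 0.3 | +1.65 | −0.71 | +2.35 |

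Weaker targeting in scenario 1 (OR 1.25) lowers the false difference to +0.44 to +1.32 mmHg. For HbA1c with an assumed SD of 2 percentage points, scenario 1 at OR 1.5 gives a false difference of +0.08 to +0.23 points. With equal rates and equal targeting, every entry is 0. That is also the result when membership is fixed before roll-out.

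Scenario 2 shows that both strata can be wrong while the comparison between them looks clean. Scenario 3 shows that similar visit rates do not establish that the strata are comparable.

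**Conditioning route.** Let visits be random, 30% in PEN and 60% in ePEN. Suppose a visit changes the outcome by δ in either arm and nothing else differs. The effect of assignment is (0.60 − 0.30) × δ = 0.30δ. Among visited households both arms have received δ, so the contrast is 0. Among unvisited households neither arm has, so it is again 0. The stratified table shows no effect although assignment has one, and no selection is involved.

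**The case against.** The strongest reply is that nothing here is shown to happen. The SAP does not say when visit status is recorded. It does not say that CHWs in ePEN make household visits, or more visits, or visits aimed at sicker households. Survey timing and the content of the CHW component are commonly left to the protocol, which is not at hand. The illustration uses no figure from the SAP, and the sign within the visited stratum changes between scenarios. Nothing is computed for the first hypothesis.

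Most of this stands, and it limits the weight of the point. It does not remove the point, because the SAP itself defines the two sub-groups, presents them as effect comparisons in all analyses, and leaves open a window that could include the intervention period.

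A reader might infer more than the text supports:

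- **That the SAP stratifies on a post-randomisation variable, or that these sub-group results are biased.** The document allows post-roll-out visits but does not specify them, and it shows no effect of arm on visiting.
- **That the main results are in doubt.** The unstratified comparisons for both hypotheses do not use visit status.
- **That the random-forest search is compromised.** That would require it to use these variables, and no inputs are listed.

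The opposite inference, that all is well if visiting is unrelated to prognosis, also goes too far. It removes selection bias but not the conditioning problem.

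**Conclusion.** The point holds as a conditional one. The two CHW-visit sub-groups are open to a definition that the assigned arm may affect. If visits are recorded after roll-out and the arm changes who is visited, the stratum effects, and possibly their comparison, are not protected by randomisation. If visits pre-date roll-out, or the arm does not change who is visited, neither problem arises.

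Sign and size are unknown. Under the assumed inputs, the selection route gives stratum errors between about −1.4 and +1.6 mmHg and a false difference between 0 and about +2.4 mmHg. Other assumptions would give other values. Five of the seven sub-group variables are not affected. Priority is minor to moderate.

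**What to change.** State in the SAP that both CHW-visit variables are defined from visits before randomisation or roll-out, give the reference date for the 12-month window, and apply the same definition to any use of them in the random forest.

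If no such record exists, remove the two variables from the list of effect modifiers. Report CHW visits by randomised arm as a process outcome, and label any analysis by post-roll-out visits exploratory and non-causal. Similar visit rates between arms should not be taken as clearance for a causal reading.

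Stating the timing or relabelling the analysis costs only wording. Using earlier visits needs a record that the SAP does not mention. If only post-roll-out visits are available, the table by visit status can no longer be presented as a causal sub-group result.
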